10.2 Serious Adverse Experiences (SAE)

An SAE is defined as any untoward medical occurrence that at any dose:

- Results in death
- Is considered life threatening (i.e., in the view of the investigator the adverse experience places the subject at immediate risk of death from the reaction, as it occurred; it **does not** include a reaction that, had it occurred in a more severe form, might have caused death)
- Requires hospital admission or prolongation of an existing hospitalization
- Results in persistent or significant disability/incapacity (i.e., a substantial disruption of a person's ability to conduct normal life functions)
- Is a congenital anomaly/birth defect
- Is an important medical event (i.e., when based upon appropriate medical judgment, the adverse experience may jeopardize the subject and may require medical or surgical intervention to prevent one of the above listed outcomes)

10.2.1 Serious Adverse Experience Reporting

All SAEs that occur after informed consent is obtained until the end of subject's participation in the study (whether Test Drug related or not) will be documented in an SAE Report. All SAEs will be reviewed by the investigator.

If only a partial SAE report is available, preliminary information will be documented on an SAE Report form, reviewed by the investigator, and reported to the PI within one business day of learning of the event. When additional relevant information is available, this information will be submitted promptly on a new SAE Report form.

Reporting of SAEs to the Independent Review Board (IRB) will be performed by the investigator in accordance with the standard operating procedures and policies of the IRB.

11 SCREEN FAILURES AND RE-SCREENING OF SUBJECTS

Subjects who fail to meet eligibility criteria at either the Screening visit or at the Baseline visit will be classified as screen failures and will not be randomized. Subjects who fail eligibility at the Baseline visit may repeat a Baseline visit, following resolution of failed eligibility criteria as applicable, within the 56 day window following the Screening visit. If the 56 day window is exceeded, the subject will be classified as a screen failure, but can be re-consented and re-screened at a later date.

12 SUSPENSION OF STUDY DRUG, WITHDRAWALS, EARLY TERMINATION PROCEDURES, AND SUBJECT REPLACEMENT

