TEST DRUG, DOSE AND MODE OF ADMINISTRATION	Flunisolide HFA (Aerospan™, MEDA Pharmaceuticals, Somerset, NJ) 1 or 2 inhalations administered via MDI twice daily for 6 weeks.

DURATION OF SUBJECT PARTICIPATION AND DURATION OF STUDY	Study visits will occur at screening, baseline, and 6 weeks (± 1 week). Total duration of subject participation will be up to 8 weeks. As enrollment will occur over approximately 12 months, total duration of the study is expected to be up to 14 months (12 months enrollment plus about 2 months for the last subjects to complete treatment).
Screening, enrollment, randomization and treatment	
Screening: At the Screening visit, a focused, standardized history and physical exam will be conducted by one of the physicians on the research team. Patients will also undergo pre and post bronchodilator spirometry. Spirometry values prior to the administration of bronchodilator will be used to assess patient's enrollment status.
 
Enrollment and Randomization: At the Baseline visit, patients will undergo a repeat focused, standardized history and physical exam. Spirometry and IOS will both be undertaken pre and post bronchodilator (in this order: IOS, spirometry, bronchodilator, IOS, spirometry).
 
Treatment: Subjects will receive treatments twice per day for 6 ± 3 days.

CONCOMITANT MEDICATIONS	
Allowed: All standard therapies
 
Prohibited: Other forms of ICS, LABAs

Efficacy Evaluations	Physiologic effects (change in lung function between baseline and end of treatment) and Clinical Effects (number of asthma exacerbations, asthma control scores) will be compared between subjects randomized to flunisolide HFA 1 inhalation BID and to flunisolide HFA 2 inhalations BID.
Primary endpoint	The average change in FEV1, FEF25-75% , R5, R5-R20, AX, Fres and X5 measured by spirometry and IOS during from baseline to end of treatment (6 ± 3 days) between subjects randomized to flunisolide HFA 1 inhalation BID and to flunisolide HFA 2 inhalations BID.
SECONDARY	The number of protocol-defined asthma exacerbations requiring

ENDPOINTS	treatment with oral steroids between subjects randomized to flunisolide HFA 1 inhalation BID and to flunisolide HFA 2 inhalations BID.
SAFETY EVALUATIONS	Rates of adverse events, withdrawal, adherence to treatment, rate of asthma exacerbations will be monitored.

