4 STUDY DESIGN

4.1 Study Overview

This is a single center, open label, parallel group trial comparing the efficacy of two different strengths of HFA flunisolide on lung function in asthma patients with small airway disease. We will enroll approximately 50 pediatric patients (ages 6-18, see discussion on sample size below) with mild to moderate asthma based upon the National Heart, Lung, and Blood Institute asthma guidelines.²¹ These patients will be recruited from new patients presenting to a pediatric pulmonary clinic as well as from general pediatric clinics associated with the University of Louisville, School of Medicine. Patients will have been steroid-naïve for at least four weeks. Prior to enrollment, patients will have demonstrated small airway disease based on pre-bronchodilator FEF_{25-75%} of less than 65% predicted.²² Patients will be randomized to receive flunisolide at either 80mcg twice a day or 160mcg twice a day with every other consecutive patient receiving alternating therapy (Figure 1). Prior to starting therapy, baseline IOS and spirometry pre and post bronchodilator (BD) will be obtained (Table 1). Patients will be randomized as described above and will be followed up at six weeks. At that point, repeat IOS and spirometry will be obtained again.

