5.2 Subject Eligibility Criteria

5.2.1 Inclusion Criteria

1. Diagnosis of asthma by pediatrician or asthma specialist
2. Informed consent by parent or legal guardian
3. 6 years to 18 years of age at Screening Visit
4. Ability to comply with medication use, study visits and study procedures as judged by the site investigator
5. FEF25-75% < 65% of predicted as a marker for small airway disease

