8.1 Overview of Evaluations and Visits

8.1.1 Screening Evaluation

At the Screening visit, eligibility for the visit will be determined by the investigator based on inclusion and exclusion criteria. All eligible subjects will undergo spirometry to ensure that baseline values fit the inclusion criteria.

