9.2 Visit 2 (Baseline) (Day 0)

Subjects who meet eligibility criteria at Visit 1 will be scheduled to return for Visit 2 no sooner than the next day but no later than 56 days following the Screening Visit. The following procedures will be completed:

1. Obtain standardized asthma control score from parent/legal guardian
2. Review current health status/medical history
3. Review concomitant medications
4. Obtain vital signs (temperature, heart rate, respiratory rate and blood pressure)

5. Measure oximetry
6. Measure height and weight
7. Perform abbreviated physical examination (Investigator)
8. Have patient perform IOS pre-bronchodilator
9. Have patient perform spirometry pre-bronchodilator
10. Have patient perform IOS post-bronchodilator
11. Have patient perform spirometry post-bronchodilator

If the subject meets all eligibility:

12. Randomize to flunisolide HFA 80mcg 1 puff BID or flunisolide HFA 80mcg 2 puffs BID
13. Dispense Study Drug and albuterol sulfate with holding chamber.
14. Review instructions for Study Drug administration
15. Schedule subject for Visit 3 (Week 6 ± 1 week)

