15.1 Analysis of Physiologic Effects (Lung Function)

The primary goal of the current study is to determine the effects of Aerospan on lung function in children with small airway obstruction. Participants recruited into this randomized parallel group study will be randomly assigned to either receive (1) 80 mcg of Aerospan twice a day or (2) 160 mcg of Aerospan twice a day, during the six-week study period. Outcomes will be measured at baseline and at six-week follow-up as described above.

First we will start with straightforward tests for differences among the two groups to test if our randomization scheme was successful. Analysis of Variance (ANOVA) techniques will be used to test for difference among continuous variables, while Kruskal-Wallis, Fischer's Exact Tests and Wilcoxon methods will be used to test for differences among categorical variables.

The primary endpoint will be changes in outcomes, over time, from baseline to six-week follow-up. The change in scores from baseline to six-week follow-up will initially be compared using paired t-tests and Chi-squared tests for trend. Repeated measurements will be analyzed using generalized linear mixed-effects regression modeling (GLMM) techniques. For continuous outcomes (e.g., FEV1, FEF 25-75%, Fres, X5, AX, R5-R20.) the identity link function and normal distribution will be used. For count data (e.g., use of Beta-agonists, episodes of

coughing, episodes of wheezing, etc.) the log link function and the Poisson distribution will be used. If we dichotomize outcomes (e.g., a Beta-agonist was used, coughing occurred, etc.) the logit link function and Bernoulli distribution will be used. Statistical analyses will be performed using SAS® Version 9.3 (SAS Institute Inc., Cary, NC).

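### The plan conflicts on whether FEF25-75 below 65% is judged at Screening only or again at Visit 2; re-applying it at Visit 2 could produce a spurious within-arm gain in FEF25-75

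*Combined protocol and SAP*

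**What the plan says.** The criterion in section 5.2.1 reads "FEF25-75% < 65% of predicted as a marker for small airway disease" and names no visit. Its neighbours do: age is fixed at Screening, and exclusions 1 to 3 in section 5.2.2 refer to both Screening and Baseline.

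Several places put the qualifying test at Screening. The synopsis, under Screening, says "Spirometry values prior to the administration of bronchodilator will be used to assess patient's enrollment status". Section 8.1.1, on the Screening evaluation, says "All eligible subjects will undergo spirometry to ensure that baseline values fit the inclusion criteria". Section 9.1 lists spirometry (item 8) before the review of inclusion and exclusion criteria (item 10). Section 4.1 is less specific: "Prior to enrollment, patients will have demonstrated small airway disease based on pre-bronchodilator" FEF25-75 under 65%.

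Two places allow the test to be applied again at Visit 2. Section 9.2 lists the Visit 2 IOS and spirometry as steps 8 to 11, then sets the condition "If the subject meets all eligibility", then randomises at step 12. Section 11 classes a child who fails eligibility at either visit as a screen failure and adds: "Subjects who fail eligibility at the Baseline visit may repeat a Baseline visit, following resolution of failed eligibility criteria as applicable", within 56 days of Screening. No criterion is exempted and no number of repeats is given. After 56 days the child may be re-consented and re-screened.

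Section 4.2 measures change in FEF25-75 from the Baseline visit to week 6. Section 15.1 states: "The primary goal of the current study is to determine the effects of Aerospan on lung function in children with small airway obstruction". It compares change first by paired t-tests. Section 15.2 states 86% power for a 10% main effect of each treatment. Both arms are active (section 7.2).

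**The concern.** Take a child at 62% at Screening and 69% at Visit 2. Under the synopsis and section 8.1.1 the child is randomised with a starting value of 69%. Under sections 9.2 and 11 the child can be held back, re-tested, and randomised once the value falls below 65%. The two readings enrol different children, and staff cannot tell which one applies.

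Under the second reading, the measurement that starts the change score must itself be low to count. Its error is then negative on average, while the week-6 error is not, so the mean change is positive with no drug effect. There is no untreated arm to reveal this. Paired t-tests within each arm, and any statement about the effect of each dose on its own, would count the artefact as response.

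**Working it through.** **The plan's own figures.** Evaluable number: 50 × 0.9 × 0.9 = 40.5, which reproduces the planned 40 (20 per arm). The 86% power cannot be reproduced because no SD is given. If the 10% effect is read as 10 points at two-sided 0.05, 86% power needs an SD of change of about 10.1 to 10.4 (two-sample, 20 per arm), 13.9 (paired, n=20) or 20.3 (paired, n=40). If change were test error alone, dividing by √2 gives a per-visit error SD of about 7 (10.1/1.414), 10 (13.9/1.414) or 14 (20.3/1.414). The plan does not say whether the 10% is relative or in points, so this only places the assumed range below.

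**Model.** Write T for a child's true value, and S = T + e1, B = T + e2, F = T + e3 for Screening, Visit 2 and week 6. Errors are independent and there is no drug effect.

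- Screening only: E[F − B | S < 65] = −E[e2 | S < 65] = 0, because e2 is independent of S.
- Re-applied at Visit 2: E[F − B | S < 65, B < 65] = −E[e2 | S < 65, B < 65], which is above 0.
- With a repeat: a child with B ≥ 65 gets a second Visit 2 test, and that value becomes the baseline if it is below 65.

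**Assumed inputs (not in the documents).** Source population in % predicted: mean 75, SD 20; or mean 70, SD 15; or a mean set so that exactly 10% fail at Screening (SD 15 or 20). Visit error SD is 8, 10 or 12 points. Each setting simulates 2,000,000 children; results agree between runs to within 0.1 point.

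| Source population | Fail at Screening | Of those passing, ≥65% at Visit 2 | Screening only | Re-applied once | Re-applied, one repeat |
|---|---|---|---|---|---|
| Mean 75, SD 20 | 67–68% | 24 / 28 / 32% | 0.0 | +1.9 / +3.0 / +4.3 | +2.3 / +3.6 / +5.0 |
| Mean 70, SD 15 | 60–62% | 27 / 32 / 35% | 0.0 | +2.3 / +3.6 / +5.1 | +2.8 / +4.2 / +5.7 |
| 10% fail, SD 15 | 10% | 5 / 6 / 7% | 0.0 | +0.5 / +0.8 / +1.2 | +0.6 / +0.9 / +1.3 |
| 10% fail, SD 20 | 10% | 4 / 5 / 6% | 0.0 | +0.4 / +0.6 / +0.9 | +0.5 / +0.7 / +1.0 |

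Triples are for visit error SD 8 / 10 / 12; changes are in points of % predicted.

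**Share due to the repeat.** In the first two rows the repeat adds 0.4 to 0.7 points (for example 5.0 − 4.3 = 0.7). Re-applying the threshold does most of the work.

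**Effect on the paired t-test (n=20, nominal 5%).** Screening only: about 5%. Re-applied with one repeat: 15 to 34% in the first two rows, 5 to 6% in the last two.

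**Wider range.** With source mean 65, 75 or 85, SD 20 and visit error SD 6, 10 or 15, one re-application gives +0.8 to +8.2 points, and up to three Baseline attempts give +1.1 to +9.8.

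**Dose contrast.** The eligibility check comes before randomisation, so both arms are selected alike. Over the same wider range, with up to three attempts, the simulated between-arm difference averages within 0.1 point of zero and the two-sample t-test rejects in 4 to 6% of trials.

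**The case against.** The strongest objection is that most of the text puts the test at Screening. Besides the synopsis and section 8.1.1, section 9.1 holds the only listed review of the criteria, section 9.2 opens by admitting only children who were eligible at Visit 1, and the synopsis gives Visit 2 spirometry no eligibility role. The repeat rule also speaks of resolution, which suits wheeze, infection or saturation. An FEF25-75 that has risen above 65% has improved, and waiting for it to fall is an odd sense of resolving. All of this stands, and it makes the Screening-only reading the more natural one. It does not remove the conflict, because sections 9.2 and 11 refer to eligibility as a whole and exempt nothing.

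The size is also open to challenge. Section 15.2 expects 10% of potential participants to be ineligible or unwilling, whereas the first two source populations have 60 to 68% failing at Screening. Matching 10% brings the artefact down to about +0.5 to +1.3 points. This stands as a lower scenario. It is itself conditional, because section 15.2 does not define its denominator, and the match needs a source mean of about 35 to 43% of predicted.

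A reader might infer that a Baseline can be repeated indefinitely until the value is low enough. The documents do not support that: repeats end 56 days after Screening, and going further needs fresh consent and a new Screening. A reader might also expect sites to diverge, but this is a single-centre trial.

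Finally, the synopsis states the aim as a dose-related difference, and within-arm change in an open-label trial without placebo cannot isolate a drug effect whatever the entry wording. That limits the harm, but sections 15.1 and 15.2 do plan within-arm testing and frame power per treatment.

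**Conclusion.** The conflict is real and should be resolved. Sections 5.2.1, 9.2 and 11 leave open a re-application of the FEF25-75 threshold to the test that starts a primary change score. If that happens, a spurious within-arm gain follows: about +0.5 to +1.3 points if only 10% fail at Screening, and about +2 to +6 points under the wider source populations. If the criterion is used at Screening only, the gain is about 0. These figures rest on assumed means, SDs and independent visit errors. If Screening error carries over to a Visit 2 held as early as the next day, some regression to the mean remains even under Screening-only use. The limiting case, one test serving as both, gives 1.4 to 12.3 points over the wider range.

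Two stronger readings are tempting. One is that both arms will show improvement from this cause. The documents support only that they could, under the less natural reading. The other is that the dose comparison is biased. It is not, provided a decision to repeat does not depend on the next allocation. The exposure is confined to within-arm claims about FEF25-75; no other primary parameter is an entry criterion.

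**What to change.** - **Section 5.2.1:** state that inclusion 5 is judged once, on pre-bronchodilator FEF25-75 at the Screening visit.
- **Sections 9.2 and 11:** state that Visit 2 FEF25-75 is neither an eligibility test nor a ground for repeating Baseline.
- **Section 4.2:** state that change is taken from the Visit 2 value of the visit at which the child was randomised.
- **Section 15.1 and the planned SAP:** make the between-dose contrast, adjusted for the Visit 2 value, the analysis that carries the conclusion. Report within-arm change, including the paired t-tests, as descriptive only. This also covers any regression to the mean left by carry-over from Screening.

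The cost is a few sentences. The downside is that some randomised children will have a Visit 2 FEF25-75 at or above 65% (4 to 35% of those passing Screening in the settings above). Report their number by arm and let the baseline adjustment handle them.

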12.1 Discontinuation of Study Drug, Subject Withdrawals, Early Termination Procedures

A subject may permanently discontinue study drug at any time if the subject, the site investigator, or the Sponsor feels that it is not in the subject's best interest to continue. If a subject discontinues treatment due to an adverse event, the subject will be followed and treated by the Investigator until the abnormal parameter or symptom has resolved or stabilized. If study drug is permanently discontinued, the participant should be encouraged to remain in the study and to complete all study visits and procedures,

The following is a list of possible reasons for discontinuation of study drug or withdrawal. Note that in the case of the second two reasons, the participant should be encouraged to complete the remaining study visits rather than withdraw:

- ◆ *subject withdrawal of consent*
- ◆ *subject is not compliant with study procedures*
- ◆ *adverse event*
- ◆ *study drug intolerance*

12.2 Replacement of Subjects

Subjects who withdraw from the study will not be replaced.

13 PROTOCOL VIOLATIONS

A protocol violation occurs when the investigator fails to adhere to significant protocol requirements affecting the inclusion, exclusion, subject safety and primary endpoint criteria. Protocol violations for this study include, but are not limited to, the following: failure to meet inclusion/exclusion criteria, or incorrectly following protocols laid out in this document. The Principal Investigator will determine if a protocol violation will result in subject withdrawal.

When a protocol violation occurs, it will be discussed with the investigator and a Protocol Violation Form detailing the violation will be generated. This form will be signed by the Investigator. A copy of the form will be filed in the site's regulatory binder.

14 DATA SAFETY MONITORING

As this is an FDA approved drug being used in approved populations at approved doses, the elements listed under "safety evaluations" as above will be tracked by the PIs but no formal data safety review board will be in place.

15 STATISTICAL METHODS AND CONSIDERATIONS

Prior to the analysis of the data, a detailed Statistical Analysis Plan (SAP) will be written describing all analyses that will be performed. The SAP will contain any modifications to the analysis plan described below.

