7 STUDY TREATMENTS

7.1 Method of Assigning Subjects to Treatment Groups

We will use a block randomization scheme to promote balance at the end of the study. Block randomization ensures that after each block of individuals are enrolled in the study (n individuals in total); an equal number of individuals will be assigned to each group (n/2 individuals in each group). We will use random block sizes of 8-12. Data about grouping will be kept by study coordinator in a secure, locked location in the clinic. A password protected electronic database will also be created to store patient data in which will be kept on an encrypted, password protected computer.

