7.2.1 Packaging and Labeling

As this is an open label study, patients will be given the device in standard packaging from MEDA Pharmaceuticals.

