16 DATA COLLECTION, RETENTION AND MONITORING

16.1 Data collection

Data that will be collected during the study include: enrollment and randomization information, spirometry/IOS data, other subject data collected during the study visit, and asthma controls scores. This data will be kept in a secure, locked filing cabinet in the pediatric pulmonary clinic office.

An electronic database of data will be created using Microsoft Excel. This database will be encrypted, password protected, and stored exclusively on a password protected computer in the pediatric pulmonary clinic.

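### In an open-label, single-centre trial the SAP need only precede analysis, so it can be written or changed after six-week results by dose are visible

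*Combined protocol and SAP*

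**What the plan says.** Section 15 gives the only timing rule for the SAP: "Prior to the analysis of the data, a detailed Statistical Analysis Plan (SAP) will be written describing all analyses that will be performed". The next sentence adds: "The SAP will contain any modifications to the analysis plan described below". The documents do not tie the SAP to first randomization, first Visit 3, data entry, database lock or access to data by arm. They require no signature or date on it, and no marking of late changes.

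Section 4.1 sets the design: "This is a single center, open label, parallel group trial comparing the efficacy of two different strengths of HFA flunisolide". Section 7.2.1 confirms that nothing is masked: "As this is an open label study, patients will be given the device in standard packaging from MEDA Pharmaceuticals". Section 7.1 adds: "Data about grouping will be kept by study coordinator in a secure, locked location in the clinic". Section 16.1 lists arm and outcome together: "Data that will be collected during the study include: enrollment and randomization information, spirometry/IOS data, other subject data collected during the study visit". These records and the database are kept in the pediatric pulmonary clinic. Under Section 14 the safety evaluations, which include exacerbations, "will be tracked by the PIs but no formal data safety review board will be in place".

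On the form of the outcomes, Section 15.1 and the synopsis leave a choice open: "If we dichotomize outcomes (e.g., a Beta-agonist was used, coughing occurred, etc".

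**The concern.** A rule that the SAP must precede analysis protects a blinded trial, because until unblinding nobody can see results by arm. Here the clinic that randomizes, dispenses and instructs by dose also measures the six-week spirometry and IOS and stores the results. Nothing separates having seen results by dose from not yet having analysed them.

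If the primary variable, the bronchodilator state, the test or the form of an outcome is settled at that stage, the choice can follow the data, and the nominal level of the chosen test is no longer its real level. Without a date on the SAP, a reader cannot establish whether a choice came before or after the results.

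**Working it through.** The plan states no figure on this point, so there is none to reproduce. The check has two parts: whether the timing gap exists, and what is left to choose within it.

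**1. Timing.** The latest SAP date Section 15 allows is just before the first analysis. The earliest date on which a six-week result exists beside a known dose is the first Visit 3, about six weeks after the first randomization. Enrolment is expected to take about 12 months (synopsis), so most of the trial can lie between these two dates. No section closes the interval.

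**2. Choices open in that interval.**

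| Choice | What the documents give |
|---|---|
| Primary variables | Seven (synopsis, primary endpoint); six (synopsis analysis plan and Section 1.7); five (Section 4.2). No ranking, no multiplicity rule |
| Bronchodilator state | Pre and post values measured at both visits (Sections 9.2, 9.3); the primary endpoint names neither |
| Decisive test | Paired t-tests and chi-squared trend tests first, then mixed models (Section 15.1); none named as decisive |
| Count or yes/no | Left conditional (synopsis, Section 15.1) |

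**3. Illustration, primary variables.** Assume no true dose difference, each variable tested at two-sided 0.05, and a claim made on any one of them. If the variables were independent, the chance of at least one significant result is 1 − 0.95^k:

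- k = 5: 22.6%
- k = 6: 26.5%
- k = 7: 30.2%

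These variables are correlated, and the documents give no correlations. With an assumed common correlation from 0.3 to 0.9, simulation gives 21.0% down to 10.2% for five and 27.0% down to 11.4% for seven.

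With one variable fixed, a free choice between two analyses and between pre- and post-bronchodilator values still gave about 12% to 14%. That run had 20 per arm, used a t-test on change or ANCOVA as stand-ins for the unnamed between-dose test, and assumed a between-visit correlation of 0.6 and a pre/post correlation of 0.8. With one variable, one state and one test fixed, the simulated error was 4.4% to 5.7%, which is the nominal level.

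**4. Illustration, a secondary outcome.** Albuterol use was simulated with 20 per arm, no dose effect, negative binomial counts with assumed means 2 to 20 and dispersion 1 to 2, and 6,000 trials per setting. The better of two p-values was taken, one from a rank test on counts and one from a test on any use. With chi-squared for any use, the error was mostly about 6% to 8% (5.4% to 8.6% over eight settings). With Fisher's exact test it was about 5% to 6%. Neither pair is the model Section 15.1 names for these outcomes, so this shows order of magnitude only.

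**5. Effect of keeping only the count.** Section 15.1 names a Poisson model for counts. Under the same overdispersed counts, a simple two-group Poisson test without a subject effect rejected a true null in about 22% to 75% of trials, depending on mean and dispersion. Removing the yes/no option while keeping plain Poisson would therefore replace a small inflation with a large one.

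**The case against.** Several safeguards exist. The SAP must precede analysis and contain its modifications, so departures from Section 15 can be found by comparing the two texts. Section 15.1 already fixes the time points and the model family and link for each type of outcome. The coordinator keeps the group list locked away. Section 17.1.2 requires IRB approval of protocol changes, with exceptions. Spirometry and IOS are instrument readings, which limits biased measurement.

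All of this stands, and it narrows the point. It does not close the gap. Comparing the texts shows that something changed, but not whether results had been seen. A locked list does not hide the dose from the clinic that dispenses it, and nobody is said to be blinded. The IRB rule sets no SAP date. Instrument readings can still be selected by variable, bronchodilator state or test.

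Three stronger readings are tempting, and the documents support none of them:

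- That the investigators will choose late, or that they watch outcomes by dose as these accrue. Section 14 says only that the safety elements are tracked; it gives no timing and no review by arm.
- That a declared trial-wide 5% error rate is breached. Two-sided 0.05 appears only in the power statement for dichotomized outcomes (synopsis and Section 15.2).
- That the albuterol illustration measures the risk to the primary conclusion. Albuterol use is secondary, and with some tests the inflation is close to nil.

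**Conclusion.** The point holds as a weakness in a stated rule. Section 15 can be obeyed exactly while the SAP is written or changed with six-week results by dose in view, and choices that matter to the primary result are open at that time. This rests on the text alone.

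The size is not established. It depends on correlations, event rates and tests that the documents do not give. The primary-variable figures (about 10% to 30% for a free choice among five to seven) and the albuterol figures (about 5% to 8%) are illustrations under stated assumptions and should not be quoted as this trial's error rate. Part of the first range also reflects the missing multiplicity rule, which an early date alone would not cure, so the SAP's content needs fixing along with its date.

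This is an inexpensive improvement that should be made. It is not evidence that any analysis has been or will be selected.

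**What to change.** - **Section 15:** require the SAP to be finalised, signed and dated before the first Visit 3. Any later change is to be dated, justified and labelled post hoc.
- **Content of that SAP:** state which variables are primary, with a multiplicity rule if more than one; the bronchodilator state; and the single decisive between-dose test. Make the synopsis, Section 1.7 and Section 4.2 agree with it.
- **Synopsis and Section 15.1:** replace the conditional wording on dichotomizing with one pre-stated form for each outcome. If albuterol use is analysed as a count, use a model that allows for overdispersion, such as negative binomial or a robust variance, in place of plain Poisson.
- **Synopsis sample-size rationale and Section 15.2:** bring the power statements for counts and dichotomized outcomes into line with the forms chosen.
- **Optional:** give the analyst files with dose coded A/B until the programs are final.

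The cost is writing the SAP earlier and giving up late flexibility. No patients, visits or procedures are added.
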